9.6.3 Physical Examinations

A complete physical examination will be conducted at Screening, Day 84, Day 119, and at the Final Visit. The number and percentage of normal and abnormal physical examinations will be summarized by body system and treatment arm at each visit. Any clinically significant physical examination findings will be reported as AEs or SAEs. Physical examination findings will also be listed for each visit.

9.6.4 Granulomas

A clinical evaluation for mass formation will be conducted at baseline, Days 1, 7, 14, 21, 28, 42, 56, 77, 84, 91, 98, 105, 112, 119, and the Final Visit. However, at any time that clinical signs and symptoms warrant, an evaluation for the potential for a granuloma will be conducted.

Signs and symptoms of an inflammatory granuloma, including radicular pain, sudden loss of drug efficacy that is not attributed to other assignable causes, and spinal cord compression at the level of the catheter tip will be monitored. If there are signs or symptoms identified which may indicate an inflammatory mass formation, an MRI (with and without contrast) or

CT scan will be performed (with consent of the subject) to evaluate the potential presence of an inflammatory granuloma as opposed to other catheter related problems that may result in reduced delivery or clinical symptoms.

All data captured with regard to possible or confirmed inflammatory granulomas will be listed, including the date of clinical evaluation for an inflammatory mass, signs and/or symptoms of the granuloma, and all MRI or CT scan results. The incidence and rate of possible granuloma, as well as, the incidence and rate of confirmed granuloma will be summarized by treatment group.

The method of inflammatory granuloma assessment will be summarized by the number and percentage of subjects in the following categories:

- Subjects with clinical signs and symptoms of a granuloma
- Subjects with clinical signs and symptoms of granuloma, but MRI/CT not performed
- Subjects with clinical signs and symptoms of granuloma, MRI/CT performed
- Subjects with confirmed granuloma by MRI/CT via independent radiologist or surgery

All signs and symptoms data related to mass formation including MRI or CT information will be listed.

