The purpose of the 12-week open label period of the trial is to titrate subjects to an optimal dose of hydromorphone hydrochloride and demonstrate the ability to maintain adequate pain relief in subjects requiring intrathecal opioid therapy. During the open label period of this trial up to Day 77, subjects may be given oral supplemental medication up to a maximum of 180 mg-equivalent morphine per day to manage pain during the titration to an optimal dose. The subject should be

weaned off this oral supplement as much as possible as the intrathecal dose of hydromorphone hydrochloride is optimized. Prior to randomization from Day 77 to 83, the goal is to demonstrate adequate pain relief without oral supplement, defined as an average VASPI score of 50 mm or less based on the last 5 days with nonmissing pain scores. During the double-blind period from Day 84 to 119, up to 60 mg per day of oral morphine-equivalence of opioid is permitted and is intended only for the purpose of managing withdrawal symptoms in subjects who may require some intervention. The 60 mg per day morphine-equivalence dose of opioid is expected to help relieve possible withdrawal effects, but is not intended to significantly impact pain. Doses of oral opioids, any change in prescription medications, or any changes to non-pharmacologic interventions intended to manage pain, will constitute treatment failure.

Given subjects on strong intrathecal opioids cannot be abruptly withdrawn, during the randomization phase one group will remain on their optimal dose of therapy, while the other control group is weaned off therapy over a 4 week period followed by 1 week at the lowest pump setting. It is anticipated that most subjects in the group whose dose of intrathecal opioids is being titrated downward will fail treatment prior to reaching a near 0% dose. The final step of the titration will be to place the pump in shipping mode, which lowers the speed to 0.005 mL/day. Subjects may rescue based on intolerable pain at any time and will be considered a treatment failure, or if their 5 day average pain intensity score is 20 mm greater than their baseline score prior to randomization they will also be considered a treatment failure.

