# 3.2.2 Secondary Endpoints

The most important secondary endpoint is:

- Safety of intrathecal hydromorphone hydrochloride as assessed through collection of AEs and SAEs during the conduct of the trial. Particular attention will be paid to:
  - Rate of confirmed granulomas that are verified by MRI with and without contrast, CT myelogram or by surgery.
  - o Rate of possible granulomas.

Other secondary endpoints include:

- Short-Form McGill Pain Questionnaire (SF-MPQ) (1).
- Time to Rescue after Randomized-Withdrawal (2, 3).
- Oral Opioid Supplement Consumption.

- Brief Pain Inventory (BPI) (4, 5).
- Patient Global Impression of Change (PGIC) (6).

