## 3.3 Diagnosis of Granuloma

The use of intrathecal morphine has been associated in rare cases with a granuloma at the catheter tip that can result in serious neurological impairment, including paralysis. These events have been reported infrequently with hydromorphone hydrochloride and are more commonly associated with use of combinations of compounded drugs or high concentration formulations. Nevertheless, the potential for a granuloma or mass will be assessed at each visit to the investigator.

Clinical signs and symptoms that may indicate a granuloma include:

- A sudden decrease in therapeutic response requiring increased daily doses that is not attributed to other assignable causes (e.g. mechanical failures, catheter movement or catheter blockages).
- Change in the character, quality, or intensity of the subjects pain (ie, is less well managed).
- o Unexplained pain at the dermatomal level of the catheter tip.
- Unexplained neurological deficit or dysfunction that could be caused by mass effect at the spinal level of the catheter tip.

For the purpose of this study to establish that there is a definite granuloma, an MRI (with and without contrast) or CT myelogram must demonstrate an intradural extra-medullary mass near the catheter tip. If only clinical signs are detected, but the granuloma or mass cannot be verified by MRI, CT myelogram or surgery, and no other cause can be determined, the event will be classified as a possible or suspected granuloma.

If in the opinion of the investigator there is a reasonable probability that the subject may be experiencing a granuloma, an MRI with and without infusion of a contrast agent or a CT myelogram will be requested. All MRI or CT myelograms will be assessed by a single central independent radiologist who will be blinded to the subject's history.

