Subjects may be given oral supplemental medication for pain up to a maximum of 180 mgequivalent morphine per day prior to Day 77 of treatment, however, the objective of the trial during this period is to achieve an optimal dose of intrathecal hydromorphone hydrochloride and reduce or eliminate any oral supplement. Oral supplement in excess of 180 mgequivalent morphine per day or other interventions due to intolerable pain, is not permitted and the subject will be withdrawn from the trial and weaned off intrathecal hydromorphone hydrochloride and converted to other appropriate pain therapies. From Day 77 to Day 119 or day of rescue, subjects are permitted up to 60 mg-equivalent morphine per day only to manage possible withdrawal symptoms.

On Day 77 the pump should be refilled with intrathecal hydromorphone and any final adjustments made to the daily dose or programming. On Day 77, the subject will be given a remote monitoring device to measure VASPI scores twice daily in the morning (5:30 am to 12:00 noon) and in the evening (6:00 pm to 11:45 pm). After Day 77 and during the randomized double-blind period there should be no dose adjustments to intrathecal hydromorphone hydrochloride other than those dictated by the protocol for subjects on the control arm who have their dose titrated downward. After Day 77, there should also be no changes to the pump programming for simple continuous, complex continuous or PTM dosing regimens until after the completion of the trial.

At the end of the 12 week continuous dosing period, subjects who meet criteria for randomization will be randomized in a 1:1 ratio to either remain at their current dose of hydromorphone or who have their dose titrated downward (control group) in a blinded fashion. The criteria for randomization is defined as an average VASPI score of 50 mm or less on a scale of 100 mm for the last 5 days with daily pain measurements prior to randomization on Day 84. After Day 77 the subject should be weaned off any oral supplement of opioid or other prescription medications prior to randomization. For those subjects randomized to be withdrawn from hydromorphone therapy on Day 84, the pump speed will be adjusted to decrease the total daily dose each 7 days (\pm 1 day), starting at a dose

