8.1 Sample Size

Approximately 150 subjects will be enrolled at up to thirty (30) US investigative sites to obtain approximately 80 subjects who qualify for randomization into the double-blind period on Day 84. This enrollment is based on a combined drop out and treatment failure (i.e. > 50 mm on a 0 to 100 mm VASPI score for the last 5 days with non-missing data prior to the double-blind period) rate of approximately 45%.

During the double-blind period, the true treatment failure rate in the hydromorphone hydrochloride arm is assumed to be at most 20%. Based on a two-sided, two-sample comparison of proportions at the alpha=0.05 level of significance, a sample size of 80 subjects (40 per arm) will provide greater than 90% power to detect an increase in the treatment failure rate of 35% (i.e., the control group who will have their dose titrated downward has a failure rate of 55%).

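### During the randomized phase, possible-granuloma and granuloma-sign counts by treatment group are open to differential misclassification, because two of the four listed signs are also expected effects of the control-arm taper

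*SAP*

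**What the plan says.** Both documents rank safety first among the secondary endpoints and name the "Rate of possible granulomas" as one of its components (Protocol 3.2.2, SAP 7.2). SAP 9.6.4 then states: "The incidence and rate of possible granuloma, as well as, the incidence and rate of confirmed granuloma will be summarized by treatment group". It also counts subjects with granuloma signs whether or not they were imaged, including the category "Subjects with clinical signs and symptoms of granuloma, but MRI/CT not performed".

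Protocol 3.3 lists four signs:

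- a sudden fall in response that needs more drug and has no other assignable cause;
- "Change in the character, quality, or intensity of the subjects pain (ie, is less well managed";
- unexplained pain at the dermatome of the catheter tip;
- unexplained neurological deficit.

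An event with clinical signs only, no verified mass and no other explanation is classed as possible or suspected. The second sign is missing from the synopsis list and from SAP 9.6.4, but the schedule footnotes in both documents send sites to Protocol 3.3. Evaluations take place at every visit from Day 84 to Day 119.

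The control arm is tapered in weekly steps to about 0% of the randomization dose. Protocol 1.4 says of it: "It is anticipated that most subjects in the group whose dose of intrathecal opioids is being titrated downward will fail treatment". An independent pump operator makes the changes, and the evaluating staff are blinded to them (Protocol 3.4.1, 3.5.1.3).

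**The concern.** Planned under-dosing can present as loss of response or worse pain, which are the first two signs on the list. The condition that should screen out such events depends on finding another cause. In this trial the most likely other cause is hidden from the person making that judgement. Neither document says that the dose record will be consulted, or that possible granulomas will be reclassified once the arm is known. The counts of subjects with signs do not apply the final no-other-cause condition at all.

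The reporting does not help the reader to separate these events. SAP Appendix A gives a single Granuloma Assessment table, 14.3.5.4, whereas adverse events, vital signs and physical examinations each have separate open-label and randomized tables. An event on a stable open-label dose and an event at 12.5% of the randomization dose would fall in the same cell.

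At stake is the reading of a named safety component. Extra possible granulomas among subjects being taken off the drug would make staying on it look protective, when they may reflect only the taper.

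**Working it through.** **Inputs.** SAP 8.1 assumes a failure rate of at most 20% on maintained dose and 55% under the taper, tested by a "two-sided, two-sample comparison of proportions at the alpha=0.05 level of significance", and says that "a sample size of 80 subjects (40 per arm) will provide greater than 90% power". Allocation is 1:1 (SAP 4). Protocol 1.3.3 cites 12 confirmed, probable or possible granulomas among 4,384 subjects under surveillance.

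**The plan's own figure.** Pooled normal approximation, 40 per arm:

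- mean rate = (0.20 + 0.55)/2 = 0.375
- null SE = √(2 × 0.375 × 0.625/40) = 0.1083
- alternative SE = √((0.20 × 0.80 + 0.55 × 0.45)/40) = 0.1009
- power = Φ[(0.35 − 1.96 × 0.1083)/0.1009] = Φ(1.37) = 91.4%

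Exact enumeration of the Pearson test gives 91.5%. The stated power reproduces, so these rates are a fair basis for what follows.

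**Expected failures.** Tapered: 0.55 × 40 = 22. Maintained: 0.20 × 40 = 8. Ratio 22/8 = 2.75.

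**Sensitivity to misclassification.** Let f be the share of failures classed as possible granuloma. The documents do not give f. It is assumed equal in both arms because the evaluator is blinded. The excess is f × (55 − 20) = 35f percentage points.

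| f | Tapered, per 40 | Maintained, per 40 | Excess (percentage points) |
|---|---|---|---|
| 0 | 0 | 0 | 0 |
| 1% | 0.22 | 0.08 | 0.35 |
| 5% | 1.1 | 0.4 | 1.75 |
| 10% | 2.2 | 0.8 | 3.5 |
| 25% | 5.5 | 2.0 | 8.75 |

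**Scale for comparison.** 12/4,384 = 0.27%. That is 80 × 0.0027 = 0.22 events among 80 randomized subjects, or 150 × 0.0027 = 0.41 among about 150 enrolled. One event in an arm of 40 is 1/40 = 2.5%, so a single misclassified event would exceed the cited frequency about ninefold. This is a guide to rarity only: all 12 cases were on morphine, six of them were themselves only possible, and surveillance ran from 2003 to 2010.

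**Limits of the proxy.** Failures are not the same as worsened pain. Failure also covers oral opioid above the permitted limit for withdrawal symptoms and changes in non-opioid or non-drug treatment. Conversely, pain can worsen without reaching the 20 mm criterion.

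**The case against.** A reader might infer that the withdrawal arm's rate is inflated by construction. The documents do not support that. Only two of the four signs overlap with the taper, and the first is narrowed to a sudden change with no other assignable cause, whereas the taper runs in weekly steps. The requirement that no alternative explanation be found governs all four signs. A blinded investigator still knows that half of the randomized subjects are being tapered and may accept that as a plausible cause. If so, f is near zero.

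A reader might also set all 30 expected failures (22 + 8) against 0.22 expected granulomas and conclude that false signals would outnumber true ones by more than 100 to 1. That compares unlike things. A recorded sign is not a possible granuloma, some failures are not pain failures, and the surveillance rate has the limits noted above.

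The summary is also descriptive, with no test. Listings of evaluations, signs, imaging and doses would let a careful reader reconstruct phase and dose. Pooling open-label events, when all subjects followed the same regimen, tends to dilute a difference between arms. For a safety count, over-inclusion is the cautious direction, which argues against any rule that removes events.

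These points limit the claim to a risk of unknown size and shape the remedy. They do not close the gap: the evaluator cannot confirm the dose cut, the documents do not say how it is to be treated, and the summary table hides when events arose.

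**Conclusion.** The concern holds as a risk of differential misclassification in Days 84 to 119. It affects the possible-granuloma rate and the counts of subjects with granuloma signs, compared by arm. The direction would favour continued drug. The size is 35f percentage points on the planning rates, from 0 at f = 0 to 3.5 at f = 10%. It assumes those failure rates, failure as a stand-in for worsened pain, and the same f in both arms. The documents give no value for f.

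The effect need not be large to matter, because one or two events would dominate so rare an outcome. Confirmed granulomas require imaging or surgery, so this mechanism does not inflate them. The point is a reporting weakness that is cheap to correct. It does not show that the safety conclusion is wrong.

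**What to change.** In SAP 9.6.4 and Appendix A:

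1. Split Table 14.3.5.4 by phase of onset: open-label, randomized by arm, and overall, as is already done for adverse events. Where no separate onset date is held, use the date of the first evaluation that recorded the sign.
2. Keep every possible granuloma in the headline count. Add a programmed sub-row for randomized-phase events that began while the subject was below 100% of the randomization dose and showed only loss of response or changed pain. Take the dose from the pump operator's record, which SAP 5 already sends for entry into the database.
3. State that the by-arm difference in this phase is not to be read as a drug effect.
4. Label the sub-row as added after unblinding. SAP 2 records that the database was locked on 18 October 2017 and that the study was already unblinded when the full analysis was resumed.

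Do not remove these events from the headline rate. Control subjects have had about 12 weeks of drug, and a real mass could present only as loss of effect. Imaging decisions stay as they are.

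The cost is some SAP wording, a little more table programming and the post-unblinding label. No new data are needed, and Appendix A already allows additions to the table list.

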Granulomas have been reported most commonly with morphine. Other drugs have also been implicated in causing this complication, including hydromorphone, fentanyl, and tramadol (11, 54, 55). Animal studies in the sheep may indicate that at equivalent daily doses (e.g. 12 mg/day) hydromorphone has less potential to induce an inflammatory mass or granuloma than morphine (21, 33). Given that hydromorphone is at least five-times more potent than morphine, these observations may explain the belief of physicians that hydromorphone has fewer side effects and potential for granuloma in that the dose and concentration at the catheter tip during infusion is far less with hydromorphone than morphine. The daily dose and concentration are considered the primary factors that induce a granuloma the lower dose and slower infusion rate resulting in a lower concentration in the area of the catheter tip, would be predicted based on these animal models to have a lower potential of granuloma formation than with intrathecal morphine.

In addition to the literature, Medtronic Inc. has conducted a large publicly available post-approval surveillance study for the SynchroMed® II Programmable Pump that also includes surveillance of various drug products delivered by IT administration. This study followed 4,384 subjects with implanted SynchroMed® II Programmable Pump drug delivery systems at fifty centers, with 3,101 subjects receiving various other IT medications for pain. This study also

included subjects receiving intrathecal morphine (Infumorph). Medtronic's study was a careful examination of inflammatory granuloma formation in subjects. An inflammatory granuloma in the Medtronic surveillance study was defined as "an intradural extra medullary mass at the catheter tip that could be visualized by enhanced MRI imaging." The criteria for diagnosing such a granulomatous mass is based on several clinical signs and symptoms: a decrease of drug effect and new radicular pain and/or cord compression, MRI findings of an enhancing mass at the catheter tip on the T-1 infusion and surgical or histological confirmation.

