Following the 5 week randomized withdrawal period, all randomized subjects may be allowed to continue on intrathecal hydromorphone hydrochloride for up to 12 months of safety evaluation by entering the open-label safety study (CNS-HYD202US). Subjects in the control group who had their dose titrated down will be first titrated back onto intrathecal hydromorphone hydrochloride as part of the CNS-HYD202US protocol. Subjects who do not experience adequate benefit or cannot tolerate intrathecal hydromorphone hydrochloride during the 12-week chronic dosing period will not enter the randomized withdrawal period of the trial, and thus not be eligible for the long term treatment protocol. Subjects who experience a drug related adverse event that requires discontinuation after randomization will also not be qualified for the long- term extension study, CNS-HYD202US. Subjects will be followed for safety for the duration of their treatment with intrathecal hydromorphone hydrochloride.

Table 1 and Table 2 contain the study schedule of assessments.

Study Procedure	Screening	Baseline	Titration			Visit Sc	hedule (Da	ys 1 to 56)		
Study Day ^a	Day ^b -14 to 1	Day ^c -3 to 1	Optional Days ^e	Day 1	Day 7	Day 14	Day 21	Day 28	Day 42	Day 56
Signed informed consent	Х									
Medical history	X									
Compete physical exam	Х									
Vital signs, Height and Weight	Х	X	Х	Х	Х	Х	Х	Х	Х	Х
Urine pregnancy test	Х	X								
$\mathrm{ECG}^{\mathrm{f}}$	X									
CBC, CMP, urinalysis ^g	X									
Concomitant medication assessment	X	Х		X	Х	Х	Х	Х	Х	X
Adverse event assessment	Х	X		Х	Х	Х	Х	Х	Х	Х
Hydromorphone HCl (Pump Refill)			X ^d	Xd						
Pump Dose Adjustment			Х	X						→
Oral Opioid (180 mg morphine-eq/day max.) ^h				X						→
Plasma concentration (PK) of Hydromorphone						Х				Х
Clinical evaluation for Inflammatory Granuloma ⁱ	X			Х	Х	Х	Х	Х	Х	Х
VASPI ^j	Х	Х	Х	Х	Х	Х	Х	Х	Х	Х
COWS ^k		Х	Х			Х				
SOWS ^k		Х	Х			Х				
SF-MPQ ^k		Х				Х		Х		Х
BPI ^k		Х				Х		Х		Х
PGIC ^k		X				Х		Х		Х

Table 1: Schedule of Study Procedures: Screening and Chronic Dosing Phase to Day 56

a. Study day is based on Day 1 defined as the first day at a therapeutic dose of intrathecal hydromorphone. There is no Day 0 in this trial. Visit days are ±2 day for Optional Titration Days and Days 1, 7, 14, 21, 28, 42 56 and 77. "Unscheduled Visits" will be considered as "Optional Days" for the purpose of study assessments.

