14.3.1.7.3 Incidence of serious Adverse tvents by System Safety 14.3.5.1.1 Vital Signs - Open Label Phase Safety 14.3.5.1.2 Vital Signs - Copen Label Phase ITT 14.3.5.1.1 Vital Signs - Randomized Phase ITT 14.3.5.2.1 Potentially Clinically Significant Vital Signs - Open Safety 14.3.5.2.1 Potentially Clinically Significant Vital Signs - Open Safety 14.3.5.2.2 Potentially Clinically Significant Vital Signs - Open Safety 14.3.5.3.1 Physical Examination Findings by Body System - Safety 14.3.5.3.2 Physical Examination Findings by Body System - Randomized Phase 14.3.5.4 Granuloma Assessment All Enrolled Subjects 14.3.6.2 Study Drug Exposure Summary - Open Label Phase Safety 14.3.6.3 Study Drug Exposure Summary - Overall Safety 14.4.1.1 Clinical Opiate Withdrawal Scale (COWS) ITT 14.4.2.1 Subjective Opiate Withdrawal Scale (SOWS) ITT 14.4.2.1 Subjective Opiate Withdrawal Scale (SOWS) ITT 14.4.2.2 Kaplan-Meier Curve for Time to Rescue ITT 14.4.2.1 Subject Demographics </th 142172	Incidence of Carious Adverse Events by Custom	Cofoty	142172	Incidence of Carious Adverse Events by Custom	Cofoty
Study Drug - OverallSafety14.3.5.1.1Vital Signs - Open Label PhaseITT14.3.5.1.2Vital Signs - Randomized PhaseITT14.3.5.2.1Potentially Clinically Significant Vital Signs - Open Label PhaseSafety14.3.5.2.2Potentially Clinically Significant Vital Signs - Randomized PhaseITT14.3.5.3.1Physical Examination Findings by Body System - Open Label PhaseSafety14.3.5.3.2Physical Examination Findings by Body System - Randomized PhaseITT14.3.5.3.2Physical Examination Findings by Body System - Randomized PhaseSafety14.3.5.3Granuloma AssessmentAll Enrolled Subjects14.3.5.4Granuloma AssessmentAll Enrolled Subjects14.3.5.3Study Drug Exposure Summary - Open Label PhaseSafety14.3.6.3Study Drug Exposure Summary - OverallSafety14.4.1.1Clinical Opiate Withdrawal Scale (COWS)ITT14.4.1.2Clinical Opiate Withdrawal Scale (SOWS)ITT14.4.2.1Subjective Opiate Withdrawal Scale (SOWS)ITT14.4.2.2Subjective Opiate Withdrawal Scale (SOWS)ITT Excluding Site 028 Assessment14.2.2.1Kaplan-Meier Curve for Time to RescueITT14.2.2.2Subject DispositionAll Enrolled Subjects16.2.1Subject DispositionAll Enrolled Subjects16.2.2Subject DispositionAll Enrolled Subjects16.2.3Implantation of Intratecal PumpAll Enrolled Subjects16.2.3Liberoy of Intractable PainAll Enrolled S	14.3.1.7.3	Incidence of Serious Adverse Events by System	Safety

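### The by-arm granuloma summary has no baseline or phase limit, so read literally it puts signs and possible granulomas from before randomization into the randomized-arm columns

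*SAP*

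**What the plan says.** The SAP plans the granuloma summary in section 9.6.4: "The incidence and rate of possible granuloma, as well as, the incidence and rate of confirmed granuloma will be" summarized by treatment group. A second summary, of how granuloma was assessed, starts with the category "Subjects with clinical signs and symptoms of a granuloma". Neither carries an onset date, a baseline reference or a phase.

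The evaluations behind both are in the same section: "A clinical evaluation for mass formation will be conducted at baseline, Days 1, 7, 14, 21, 28, 42, 56, 77, 84", then Days 91, 98, 105, 112, 119 and the Final Visit. SAP Table 1 marks the row "Clinical evaluation for Inflammatory Granuloma" at Screening, not at Baseline; either one precedes study drug.

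Appendix A lists one table: "14.3.5.4 Granuloma Assessment All Enrolled Subjects". Under SAP 9.1, enrolled subjects are those who consented and received study hydromorphone, so this is close to the Safety population. SAP 6 assigns safety columns by treatment received, withdrawal or continuation, and puts subjects who never reach randomization in the overall column only.

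Other safety data are limited in time:

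- Adverse events must start or worsen after first study drug (SAP 9.6.1).
- Appendix A separates adverse event, vital sign, physical examination and exposure tables into open-label and randomized phases.
- COWS and SOWS have single tables, but SAP 9.7 presents them by visit and as change from Day 84.

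**The concern.** The rates of possible and confirmed granuloma are named under the most important secondary endpoint (Protocol 3.2.2, SAP 7.2). With no time limit, three things can go wrong.

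1. Subjects may arrive on intrathecal morphine, and the protocol notes: "Granulomas have been reported most commonly with morphine". A sign already present at the pre-drug evaluation would be counted as a sign on hydromorphone.
2. A subject with a possible granuloma on Day 28, at full dose, who is later randomized to the taper would be counted in the withdrawal column, although the finding arose before the arms differed.
3. Subjects who are not randomized appear only in the overall column, so no column shows new open-label findings among all exposed subjects.

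A reader comparing the arm columns would therefore be looking partly at findings that neither randomized treatment could have caused. Dilution in a safety table tends to hide a difference.

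**Working it through.** The plan gives no rate or precision figure for granuloma, so there is none to reproduce. The check is a count of evaluations, followed by an illustration with assumed rates.

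**Evaluations (SAP 9.6.4).**
- Before Day 84: baseline and Days 1, 7, 14, 21, 28, 42, 56, 77 = 9.
- Day 84: 1. I take it as preceding the first dose change.
- After: Days 91, 98, 105, 112, 119 and the Final Visit = 6.
- Share before any arm difference: (9 + 1)/16 = 62.5%. Without Day 84 it is 9/16 = 56%.

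**Follow-up time.** Day 1 to Day 84 is 83 days and Day 1 to Day 119 is 118 days; 83/118 = 70%. Optional titration before Day 1 would raise this share.

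**Columns (SAP 8.1 and 6).** With about 150 enrolled and 80 randomized, about 150 − 80 = 70 subjects appear in the overall column only.

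**Dilution.** The documents give no sign rates, so these are assumptions. Let q be the proportion with a sign before randomization, equal in both arms on average, and p the proportion with a sign after randomization, independent of q. An unrestricted column then shows 1 − (1 − q)(1 − p). Take p = 2.5% on continued dose and 10% on taper, with 40 per arm: 1 against 4 subjects, ratio 4.0, difference 7.5 percentage points.

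| q | Continued | Taper | Ratio | Difference (points) | Share of continued-dose column from before randomization |
|---|---|---|---|---|---|
| 0% | 1.0 | 4.0 | 4.00 | 7.5 | 0% |
| 5% | 3.0 | 5.8 | 1.97 | 7.1 | 68% |
| 10% | 4.9 | 7.6 | 1.55 | 6.75 | 82% |
| 20% | 8.8 | 11.2 | 1.27 | 6.0 | 91% |

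For q = 5%, the continued-dose entry is 40 × [1 − 0.95 × 0.975] = 2.95 and the taper entry is 40 × [1 − 0.95 × 0.90] = 5.8. The ratio collapses, while the difference shrinks only by the factor (1 − q).

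**Likely event numbers.** Protocol 1.3.3 cites a surveillance study with 12 confirmed, probable or possible granulomas in 4,384 subjects, or 0.27%. Applied to this trial, that gives 80 × 12/4384 = 0.2 events among randomized subjects and 150 × 12/4384 = 0.4 among all enrolled. Follow-up there differed, so this is only an order of magnitude. On that footing the row for signs is the one likely to hold enough events for dilution to show.

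**The case against.** The case against has several parts, and much of it stands.

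- **Confirmed granulomas.** Protocol 3.3.1 discontinues a subject in whom a granuloma is detected, so one found in the open-label phase should reach only the overall column. This stands. No such rule is stated for possible granulomas, which Protocol 3.3 defines by clinical signs without verification or another cause.
- **Silence.** A reader might infer that the SAP prescribes counting pre-drug signs. It does not. The endpoint section places granuloma rates under safety assessed through adverse events, the adverse event analyses default to treatment-emergent events, and incidence ordinarily means new cases. But SAP 9.6 names granuloma rates alongside adverse events, not among them, so the text leaves the matter open.
- **Filters.** A Day 28 case must still average 50 mm or less on VASPI to be randomized, and signs prompt imaging. Such cases are fewer, not excluded.
- **Descriptive summary.** No test, ratio or interval is planned, and few events are expected. This stands and limits the size of the point.
- **Onset.** SAP 9.6.4 promises evaluation dates in the listings; sign onset dates are not shown to be collected. This stands.
- **Attribution after randomization.** A mass found on Day 91 may reflect 12 weeks at full dose, and the taper itself can produce loss of effect. This stands and calls for a table note.
- **Appendix A.** The table list is provisional and granulomas reported as adverse events also reach the phase-split tables. True, but neither supplies a limit for Table 14.3.5.4.

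**Conclusion.** The point holds for signs and possible granulomas. Followed literally, SAP 9.6.4, the column rule in SAP 6 and the single Table 14.3.5.4 put findings from before study drug and from open-label full dose into randomized-arm columns; 10 of 16 named evaluations precede any arm difference. Confirmed rates by arm are little affected.

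Two stronger readings are tempting. One is that the arm comparison is biased in a particular direction. Pre-randomization findings are balanced on average by randomization, so what follows is dilution and chance imbalance with about 40 per arm. The other is a fixed loss, such as a true doubling after randomization appearing as (83 + 2 × 35)/118 = 1.30. That assumes a constant background rate found nowhere in the documents, and a rate ratio the SAP does not plan. The dilution table above likewise rests on assumed rates.

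No primary result changes. The point is worth correcting because it concerns how events are attributed for a named safety endpoint, and the correction is nearly free.

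**What to change.** Revise SAP 9.6.4 and Table 14.3.5.4, using the evaluation dates already in the listings:

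1. Show signs present at the pre-drug evaluation (Screening or baseline) in a separate row.
2. Add an open-label panel pooled over all exposed subjects, and a randomized-phase panel by arm. Limit the latter to signs, possible granulomas and confirmed granulomas first recorded after randomization. Give each panel its own denominator.
3. Keep an overall total.
4. Add a note that a mass found soon after randomization may reflect earlier full-dose exposure, and that loss of effect may reflect the taper.

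Where onset is not captured, first recorded date stands in for it; unknown dates can follow the SAP 9.6.1 default for adverse events. The cost is SAP wording and one more table panel, with no new data and no change to the locked database. SAP 2 says the study is already unblinded, so the study report should say when the split was specified.
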